4.8.6 Preterm formula

For infants randomised to receive PTF, Nutriprem 1 will be used (Cow and Gate Nutriprem 1) as this is in standard use in the Chelsea and Westminster neonatal unit. If an infant is allocated to the PTF intervention, then the instruction only to use PTF to supplement MOM will be made on the infants feeding plan.

4.8.7 Assumed intakes

For comparison purposes the following table illustrates the macronutrient daily intakes for a 1kg baby on 180ml/kg/d for different milks, based on mean macronutrient content from a large number of samples (415 sequential samples from 273 donors) of banked donor milk (55) and the widely accepted values taken from the mean of a number of studies of milk from mothers of preterm infants (56). This is compared with the ESPGHAN 2010 recommended intakes (51).

Table 1. Assumed intakes compared with recommendations

| | 180ml of unfortified Mother's Own Milk (MOM) | 180ml of unfortified Donor milk | 180ml of fortified MOM | 180ml of fortified Donor milk | 180ml of Nutriprem 1 | ESPGHAN 2010 Recommendation unit/kg/d |
|----------------------------------|--|---------------------------------|------------------------|-------------------------------|----------------------|---------------------------------------|
| Protein (g) | 2.7 | 2.2 | 4.7 | 4.4 | 4.7 | 4.0-4.5 * 3.5-4.0** |
| Carbohydrate (g) | 12.4 | 14.0 | 17.3 | 18.9 | 15.1 | 11.6-13.2 |
| Fat (g) | 6.3 | 5.8 | 6.3 | 5.8 | 7.0 | 4.8-6.6 |
| Energy (kcal) | 117 | 117 | 144 | 144 | 144 | 110-135 |
| Protein/Energy ratio (g/100kcal) | 2.3 | 1.9 | 3.3 | 3.1 | 3.3 | 3.6-4.1* 3.2-3.6** |

*For infants <1kg

** For infants 1-1.8kg

4.9 Trial observations, tests and investigations

4.9.1 Electronic data capture

The intention is to minimise the burden of data collection by utilising the National Neonatal Database; mortality, necrotising enterocolitis, blood-stream infection, growth, breast feeding at discharge and health resource utilisation (length of stay; intensive, high dependency and special care days, parenteral nutrition use) will be evaluated to discharge in all randomised babies; these data will be retrieved from the National Neonatal Research Database; this is created at the Neonatal Data Analysis Unit from electronic records captured at the point of care on all admissions to neonatal units nationally; the Neonatal Data Analysis Unit is based at Chelsea & Westminster Hospital and led by [name]. Data will be retrieved electronically from the Neonatal Data Analysis Unit except that stated otherwise below.

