2.4 Importance to the NHS

Infant nutrition studies involving randomisation, testing causality and unravelling biological mechanisms are rare. Yet infant nutrition is a cardinal candidate effector of long-term health. Current practice in feeding the preterm infant invariably involves the use of fortified Human Donor Milk or Preterm Formula. There are however no national standards or guidelines for enteral feeding of extremely preterm infants, and clinical practice is very variable.

Advocates of pasteurised HDM believe this is as efficacious as MOM in reducing two of the most feared conditions in newborn medicine, necrotising enterocolitis and bloodstream infection, and in improving long-term metabolic health. These result in major health services utilisation costs and a life-long burden of impairments on survivors.

An adequately powered trial is required to address these outcomes but poses two major hurdles, recruitment of large numbers of babies, and long-term follow-up. The organisation of NHS neonatal specialist care and the establishment of the Neonatal Data Analysis Unit that holds and archives national neonatal data at Chelsea & Westminster Hospital, and has received permission for the National Information Governance Board to link this to Hospital Episode statistics data, offers unique international opportunity to conduct this trial in the UK and achieve long term follow-up at low cost. Clarification of efficacy will advance clinical care, and enable economic evaluation and rational development of Human Milk Banking.

3. Aims and Hypothesis

Specific aims of this pilot trial are to:

A: Assess feasibility

- 1) test the acceptability of the trial design with parents and clinicians
- 2) test that recruitment to target is achievable, estimate consent and dropout rates
- 3) estimate the trial requirement for HDM from NHS Human Milk Banks
- 4) test that clinical outcome data can be retrieved from operational NHS electronic records, thus minimising the burden of data capture and facilitating the use of linked NHS records to achieve long-term follow-up at low cost.

B: Obtain data on the magnitude of effect at term equivalent age and again at term plus 6 weeks of age, on key mechanistic outcomes:

- 1) the primary outcome of total body adiposity, addressing the null hypothesis: there are no differences in total body adiposity, as measured by whole body MRI, between infants randomised to receive fortified MOM+/-HDM, unfortified MOM+/-HDM, or MOM+/-PTF.

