4.1 Design

This will be a pilot single centre randomised controlled trial. There will be no novel interventions, merely randomisation of infants to three existing, widely used, standard feeding practices. For the purposes of clarity, this study will be in two parts. The first part will involve an opt out of feeding randomisation. Eligible preterm infants will be randomised by 48 hours to receive unfortified Mother's Own Milk (MOM) +/- Human Donor Milk (HDM), fortified MOM +/- HDM, or MOM +/- Preterm Formula (PTF), where HDM or PTF are used to make up any shortfall in MOM. Anthropometric and blood pressure outcomes will be determined from routinely collected clinical data. The second part will involve informed consent for collection and analysis of urine, stool, and blood samples and magnetic resonance imaging scans. The flowchart illustrates exactly what is involved if an infant is in the study.

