4.6 Randomisation

Randomisation will be generated centrally using a computer program, with minimisation by infant sex, gestational age (25-27+6 wks, 28-31+6 wks) birth-weight Z score (<-1.28, >-1.28) Randomisation will take place between 24-48hrs of age. Infants will be randomised to receive either HDM or PTF to make up any shortfall in Mother's Own Milk (MOM) until 34+6 weeks postmenstrual age. Blinding of the intervention is not practicable because of the distinctive appearances of human milk and formula, and the method of administration to preterm babies by syringe and nasogastric tube. At 35 weeks, the infant will be close to discharge, and feeding will be directly from the breast or formula by bottle in accordance with maternal choice.

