4.9.6 Weekly evaluations

Performed weekly until discharge from NICU

- Weight (when not on PN)
- Length
- Head circumference
- Diastolic blood pressure
- Systolic blood pressure
- Record any episode of suspected or confirmed NEC
- Record any episode of blood stream infection (blood culture positive)

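### Growth has no defined comparison at 34+6 weeks, when the randomised feed ends, although the data for all randomised infants are already collected

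*Combined protocol and SAP*

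**What the plan says.** **Outcome and source.** Weight, length and head circumference are a secondary outcome in section 1, with no time point, and appear again under Aim B2 in section 3. Section 4.1, describing the part of the study that covers every randomised infant, says: "Anthropometric and blood pressure outcomes will be determined from routinely collected clinical data".

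**Data window.** Section 4.9.1 lists growth with mortality, necrotising enterocolitis, bloodstream infection and length of stay, and says these "will be evaluated to discharge in all randomised babies". Section 4.9.6 schedules weight, length and head circumference: "Performed weekly until discharge from NICU". Section 4.9.4 collects all three at birth.

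**Ages named for the effect estimates.** Aim B reads: "Obtain data on the magnitude of effect at term equivalent age and again at term plus 6 weeks of age". Section 4.9.9 takes anthropometry at the two scan visits. Scans belong to the second part of the study, which needs its own consent (sections 4.1 and 4.4). Infants who die before discharge or are too unstable are not scanned, and parents may withdraw (section 4.7.2). Section 4.9.8 ties the first scan to discharge, not to a fixed age.

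**The randomised feed.** Section 4.6 has the allocated milk used "to make up any shortfall in Mother's Own Milk (MOM) until 34+6 weeks postmenstrual age". From 35 weeks, "feeding will be directly from the breast or formula by bottle in accordance with maternal choice".

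**Analysis.** Section 4.11.2 specifies regression and ANOVA for outcomes in general. It gives no age, summary measure or z score for growth, and it leaves birth-weight z score, sex and gestational age to the randomisation.

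**The concern.** The background (sections 2.2.4 and 2.2.5) expects slower growth on human milk than on preterm formula, and growth is an outcome of the main trial that this pilot is meant to inform. The most direct estimate of the feeding policies' effect on growth is at the end of the randomised feed, in everyone randomised. The plan collects what is needed for that estimate but does not define it.

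The ages it does name fall after feeding has passed to maternal choice, and research measurements then exist only in the scanned subset. The routine series runs to discharge with no stated age for the comparison. If an analyst settled on raw size at discharge, growth would be mixed with age at discharge. That age is set after randomisation and may itself depend on feeding and growth; section 4.9.1 lists length of stay as an outcome in its own right. Leaving the age open also means that it could be chosen after the data are seen.

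**Working it through.** **1. The plan's own attrition figure.** Section 4.11.1 needs 22 scanned infants per arm and allows 10% mortality before term and 10% drop-out.
- 22 / (0.9 × 0.9) = 27.2, rounded up to 28. This reproduces the plan's 28 per arm.
- Expected scans: 66 of 84 randomised = 78.6%. No separate allowance is made for parents who decline the second part.
- The power figures in section 4.11.1 are for adiposity. The documents give no standard deviation or target difference for growth, so no power for growth can be computed.

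**2. Time off the allocated feed at the named ages.** The feed ends at 34+6 = 244 days. The documents do not define term in weeks, so a range is shown.

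| Age at measurement | Days after 34+6 |
|---|---|
| 37+0 (259 days) | 15 |
| 40+0 (280 days) | 36 |
| 42+0 (294 days) | 50 |
| 40+0 plus 6 weeks (322 days) | 78 |

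The first gap may be shorter still. Section 4.9.8 places scan 1 soon after discharge, and section 4.6 describes infants at 35 weeks as near discharge.

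**3. Share of time from birth spent in the allocated-feed window, with term at 40+0.** This is an upper limit, since randomisation is at 24-48 hours.
- Born at 25+0 (175 days): 244 − 175 = 69 days; 69 / (69 + 36) = 66% at term; 69 / (69 + 78) = 47% at term plus 6 weeks.
- Born at 31+6 (223 days): 244 − 223 = 21 days; 21 / (21 + 36) = 37% at term; 21 / (21 + 78) = 21% at term plus 6 weeks.

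These are shares of exposure time. They do not measure how much of an effect is lost.

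**4. Precision from using all randomised infants.** With equal standard deviations, interval width is proportional to 1/√n.
- Infants at the scan: 28 × 0.9 × 0.9 = 22.68 per arm.
- At 34+6 weeks, if no deaths have yet occurred and all infants are measured: 28 per arm. √(22.68/28) = 0.90, so intervals are about 10% narrower.
- At 34+6 weeks, if all the assumed deaths have already occurred: 28 × 0.9 = 25.2 per arm. √(22.68/25.2) = 0.95, so intervals are about 5% narrower.
- Incomplete consent to the second part would lower the scan count and raise the gain. The documents give no rate for it.

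**5. Precision from the birth value.** Minimisation uses birth-weight z score only as a two-level factor cut at −1.28. Adjusting for the continuous birth value multiplies residual variance by about (1 − r²), where r is the correlation between the birth and later measures. The documents give no r, so no figure is put on this.

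**The case against.** **Section 4.9.1 does not set a comparison at discharge.** A reader might infer that the plan compares growth at discharge and is therefore confounded by age. The text does not say so: it states how far records are retrieved, and section 4.9.6 yields a weekly series. This stands. The gap is an undefined comparison, not a wrong one. Nor can a bias in grams be stated, since that would need raw weights, a difference between arms in discharge age and a rate of weight gain, none of which the documents give. Age-standardised z scores would remove most of the problem even at discharge.

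**The later ages are deliberate.** Section 4.9.8 wants to know whether effects persist, and comparing arms at term is still an intention-to-treat comparison whatever feeding followed. This also stands. A reader might infer that the effect at the scan is diluted by a known amount, but only the loss of exposure follows from the documents. The later measures should stay; 34+6 weeks adds a different and more direct question.

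**The gap may be short.** If well infants go home soon after 35 weeks and are scanned promptly, scan 1 may be close to 34+6 weeks for them. True, but timing then varies with illness and discharge, and the infants without a scan are still missing.

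**34+6 weeks is not fully common either.** Some infants will have died, transferred or gone home, and the documents give no proportion. This stands and calls for an explicit rule. Using age at discharge as a covariate would bring back a post-randomisation variable.

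**Growth is secondary in a feasibility pilot.** Agreed; this limits the weight of the point.

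**Conclusion.** The point holds as a cheap improvement. No stated number is wrong and the primary outcome is untouched. The plan names only term equivalent age and term plus 6 weeks for anthropometry. Research measurements at those ages come from an expected 22 of 28 infants per arm, before any refusal of the second part. They follow 36 days of unrandomised feeding if term is 40+0 (15 to 50 days for 37+0 to 42+0, possibly fewer given the discharge-linked first scan). A comparison at 34+6 weeks can be made from data already collected.

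The extra infants narrow intervals by about 5-10%. This rests on the plan's 10% and 10% attrition, on how many deaths precede 34+6 weeks, and on near-complete weekly measurement. The gain is larger if scan consent is incomplete. The main benefit is a growth estimate at the end of the randomised feed in the randomised population. The documents do not support saying that growth is compared at discharge, that a particular bias arises, or that a stated share of the effect is lost by the scan.

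**What to change.** In Aim B2 and section 4.11.2, add an intention-to-treat comparison of weight, length and head-circumference z scores near 34+6 weeks postmenstrual age in all randomised infants:

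- Use the weekly value nearest 34+6 weeks, with the z score calculated for actual age at measurement, and name the growth reference. With weekly measurement the nearest value should lie within about 3.5 days (7/2) for infants still in the unit.
- Adjust for the same measure at birth (section 4.9.4) and for the minimisation factors.
- State how infants who die, transfer or go home before 34+6 weeks are handled. One option is a mixed model of the weekly z scores, with deaths reported separately by arm. Do not rely on age at discharge as a covariate.
- Keep scan-visit anthropometry as later time points for persistence. Reconcile Aim B's fixed ages with the discharge-linked first scan in section 4.9.8.

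The cost is wording and one extra analysis time point for a secondary outcome. No new visit, sample or consent step is needed, because the birth and weekly values are already part of the routine data.

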4.9.2 Case report form

Randomisation data and certain clinical data will be collected on a case report form which will be stored securely at the neonatal data analysis unit. Only the research team will have access to the case report form.

4.9.3 Randomisation

- Study number
- Date and time of birth
- Gender
- Confirmation of eligibility (full eligibility check)
- Date of parental consent
- Name of person taking consent
- Gestational age (in weeks and days)
- Recruiting hospital
- Allocated trial intervention (HDM or PTF)

4.9.4 Baseline evaluation

- Birth weight (kg)
- Birth length (cm)
- Head circumference (cm)
- Ethnicity (NHS ethnicity)
- Mother's date of birth
- Mother's ethnicity
- Mother's height and weight (collected on case report form)
- Father's ethnicity
- Father's height and weight (collected on case report form)
- Mode of delivery
- Use of antenatal steroids
- Diastolic blood pressure
- Systolic blood pressure
- Medical conditions and perinatal medications
- Metabolomic profile (urine and stool) after informed consent

4.9.5 Daily evaluations

Performed daily until discharge from NICU

- Record nutritional intake (parenteral nutrition, daily volume of MOM, daily volume of trial feed – all collected on case report form)
- Record level of care (BAPM 2001 criteria)
- Record if infant is nil by mouth and reason for this (collected on case report form)
- Record of withdrawal information (collected on case report form)
- Weight (when on parenteral nutrition)

4.9.6 Weekly evaluations

Performed weekly until discharge from NICU

- Weight (when not on PN)
- Length
- Head circumference
- Diastolic blood pressure
- Systolic blood pressure
- Record any episode of suspected or confirmed NEC
- Record any episode of blood stream infection (blood culture positive)

4.9.7 Pre-discharge evaluations

- Metabolomic profile (urine and stool)

Performed with routine weekly bloods as close as possible to discharge and when on 3hrly feeds:

- Blood fasting (pre feeding) insulin and glucose (QUICKI), each 0.5ml volume.
- Blood for microRNA profiling 0.5ml in volume.

4.9.8 Magnetic Resonance Investigations (MRI and MRS)

Infants will undergo two magnetic resonance investigations, according to a well-defined and well established protocol (57-59). The first investigation will be as soon as possible after discharge. To investigate whether early feeding impacts on body composition

changes which persist beyond discharge, a second scan at around a corrected gestational age of term plus 6 weeks will be performed. This protocol has been used for over a decade in a large number of preterm and term infants. The MRI measurements are carried out during normal sleep without the need for sedation. All the MRI measurements (brain volume, body composition, and hepatic MRS) take a total of about 20-25 minutes. Both quantity and distribution of adipose and non-adipose tissue will be assessed. The infants will be monitored with pulse oximetry and a trained neonatal doctor will be present throughout the scan. Parents are invited to be present in the console room.

4.9.9 Scan visits

Data will be collected at each scan visit on the following:

- Weight
- Length
- Head circumference
- Feeding data (see below)
- Urine and stool for metabolomic profile

Urine samples (1 ml, from cotton wool placed in the nappy), and stool specimens (from the nappy) will be collected immediately after recruitment and at both scan appointments. All samples will be analysed at Imperial College using high throughput techniques employing in vitro NMR. This aspect of the proposed research will be supervised by [name], a leading international authority in the field.

4.9.10 Feeding data

At each scan visit, data will be collected on breast/expressed breast milk and formula feeding from end of feeding intervention to time of scan. Breast feeding will be defined according to the criteria recommended by Labbock et al (60) and subsequently adopted by the World Health Organisation. Feeding will be defined as:

1. Full breast/expressed breast milk feeding (including exclusive and almost exclusive)
2. Partial - High breast/expressed breast milk feeding (>80%)
3. Partial - Medium breast/expressed breast milk feeding (20-80%)
4. Partial - Low breast/expressed breast feeding (<20%)
5. Full formula feeding (including token breast/expressed breast milk feeding)

To avoid recall bias, parents will be given a simple feed diary to complete during the study period. Furthermore date of first formula feed, when first predominantly formula fed and when exclusively formula fed will be recorded. Parents will be asked about method of feeding at both scan points and at all contact points throughout the study period (eg telephone contact to arrange appointment for MR studies).

4.9.11 Schedule of investigations

Table 2. Schedule of investigations

| Evaluation | Baseline | Daily | Weekly | Pre-discharge | Scan 1 | Scan 2 |
|-----------------------------------|-----------------|--------------|---------------|----------------------|---------------|---------------|
| Informed Consent | + | | | | | |
| Eligibility | + | | | | | |
| Randomisation | + | | | | | |
| Weight | # | #* | ### | | + | + |
| Length | # | | # | | + | + |
| Head circumference | # | | # | | + | + |
| Blood pressure | # | | # | | | |
| Nutritional intake/feeding data | + | + | + | | + | + |
| Efficacy | | | | | | |
| Whole body MRI, MRS | | | | | + | + |
| Metabolomic Profile | | | | | | |
| Urine and stool sample | + | | | + | + | + |
| QUICKI | | | | | | |
| Fasting blood insulin and glucose | | | | + | | |
| microRNA | | | | | | |
| Blood | | | | + | | |

Key

+Research evaluation #Routine care evaluation *When on parenteral nutrition

**When not on parenteral nutrition

4.10 Assessment of feasibility

4.10.1 Trial design peer review

The trial protocol has had extensive peer review from the Neonatal Clinical Studies Group at the National Institute of Health Research Medicines for Children Research Network, on two separate occasions. This process has involved trial redesign and further review, resulting in favourable support for this feasibility trial.

4.10.2 Trial acceptability to parents

Trial design has also been reviewed at the parent research forum in the 'Medicines for neonates' programme – a National Institute of Health Research funded Research Programme, led by [name]. This programme includes several interrelated projects, one of which is 'Data sharing in Neonatal Services': understanding parents' attitudes towards the use of NHS data for research purposes in the context of neonatal services. The parent research forum involved parents who have previously had preterm

babies in the neonatal unit, and their feedback has proved invaluable in the redesign of the protocol, parent information leaflet, and consent form.

4.10.3 Trial design feedback from other sources

Trial design has also been reviewed by experts in the field by the neonatal nutrition club, and peer review from grant, and training fellowship applications. Human donor milk banks and the charity BLISS (Breastfeeding and Lactation Information Support Source) have also been involved in the trial design.

4.10.4 Recruitment to target

This feasibility study will test if recruitment to target is achievable; a conservative estimate is that 50% of eligible preterm infants will be recruited; the intention is to demonstrate that 2-4 eligible babies per month will be recruited (this would enable recruitment of 4000 babies from 40 centres over 25-50 months).

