5.1 Regulatory framework

5.2 Research ethics approval and monitoring

5.3 Adverse events

5.4 Indemnity

5.5 Sponsor

5.6 Funding

5.7 Audit

5.8 Study Management

5.9 Publication policy

5.4 End of trial

6. References

1. Protocol summary

| | |
|----------------------------------|---|
| Title | A pilot randomised controlled trial of fortified Human Donor Milk (HDM), unfortified HDM, or Preterm Formula (PTF) in preterm babies, to make up any shortfall in the volume of Mother's Own Milk (MOM) |
| Study Centre | Chelsea and Westminster Hospital Neonatal Unit |
| Study Objectives | 
 1. To assess the feasibility of a multicentre trial addressing short term (Necrotising Enterocolitis and Bloodstream Infection) and long term (growth and metabolic) outcomes 2. To address the null hypothesis: there are no differences in total body adiposity, as measured by whole body MRI, between any groups of infants randomised to receive unfortified MOM+/-HDM, fortified MOM+/-HDM or MOM+/-PTF 3. To assess the macronutrient content of HDM given to each infant in the HDM arms by analysis of HDM samples |
| Study Design | Single centre unblinded randomised controlled trial |
| Study Population | 
Inclusion Criteria
 
 • Preterm infants born between 25+0 to 31+6 weeks gestational age 
Exclusion Criteria
 
 • Major congenital or life threatening abnormalities or congenital abnormalities that preclude early milk feeding • Inability to randomise infant within 48 hours |
| Intervention | 
Either
 
 1. HDM, fortified with standard commercial multicomponent breast milk fortifier, once enteral intake of 150ml/kg/d reached, to supplement MOM 
Or
 
 2. Unfortified HDM to supplement MOM |
| Comparator | PTF to supplement MOM |
| Target number of patients | 84 (28 in each group) |
| Randomisation | 
 • Using minimisation • Stratifying factors are: gestational age (25-27+6 w and 28-31+6 w), birth weight z score (<-1.28, >-1.28) and sex |
| Primary outcomes | 
 • Total body adiposity, as measured by whole body MRI, at term equivalent age |

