4.4 Screening and enrolment

For part one of the study, we plan to randomise all eligible infants, unless explicitly requested by the parents for their baby not to take part. Where possible parents will be approached before delivery, and the study explained to them eg for mothers at risk of premature delivery. In all cases, the study will be explained to the parents by one of the clinical team or study investigators shortly after birth, and a written parent information leaflet (PIL pt 1) will be given to the parents. This process will be documented in the infant's medical notes by the person explaining the study, with a confirmation sticker. Randomisation to one of the three feeding arms will take place between 24-48hrs of age.

[figure not shown]
For part two of the study, parents will be approached by one of the clinical team or the study investigators after 48hrs of age, and part two of the study will be explained to them, with a written parent information leaflet (PIL pt 2) given to them. At a convenient time for the parents, informed consent will then be sought for part 2 of the study. All infants will be recruited from the Chelsea and Westminster Hospital Neonatal Unit.

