4.10.6 Electronic outcome data capture

Test that outcome data can be retrieved from operational NHS electronic records, thus minimising the burden of data capture and facilitating the use of linked NHS records to achieve long-term follow-up at low cost; data will be captured as detailed above in all randomised babies to discharge. The National Neonatal Research Database is created at the Neonatal Data Analysis Unit from electronic records captured at the point of care on all admissions to neonatal units nationally; the Neonatal Data Analysis Unit is based at Chelsea & Westminster Hospital and led by [name].

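### The 25-50 month projection for the 4000-infant trial holds only if 40 centres average the pilot unit's recruitment rate, which a single-centre pilot cannot show

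*Combined protocol and SAP*

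**What the plan says.** The first study objective in the protocol summary (section 1) begins "To assess the feasibility of a multicentre trial". Section 2.1 explains that the pilot is to inform a funding application for a UK trial of about 4000 babies.

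On recruitment, section 4.10.4 offers three figures:
- An expected uptake: "a conservative estimate is that 50% of eligible preterm infants will be recruited".
- A rate to be shown, followed in parentheses by what it implies: "the intention is to demonstrate that 2-4 eligible babies per month will be recruited (this would enable recruitment of 4000 babies from 40 centres".
- The duration that completes the parenthesis: 25-50 months.

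The pilot itself has one site. Section 4.1 states: "This will be a pilot single centre randomised controlled trial". Section 4.4 adds: "All infants will be recruited from the Chelsea and Westminster Hospital Neonatal Unit". Section 4.3.1 further restricts entry to infants whose mothers live in one neonatal network.

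Sections 2.4, 4.9.1 and 4.10.6 describe a national research database, built by a data unit at the pilot hospital from "electronic records captured at the point of care on all admissions to neonatal units nationally". Section 4.8.5 mentions a growth reference for infants under 32 weeks, co-ordinated by the same data unit, using routine data from 113 UK units and stratified by week of birth gestation. Aim A2 in section 3 includes estimating consent and dropout rates.

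**The concern.** A unit's monthly recruitment is its number of eligible admissions multiplied by the fraction recruited. The first factor depends on that unit's size and referral pattern. Multiplying the product by 40 assumes that the other centres match it on average, and nothing in the documents gives a reason why they would. With a single site, the pilot also yields no estimate of how much centres vary.

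The projected duration bears directly on the first objective and would be a natural figure to carry into the funding application. The pilot could recruit at the stated rate while the main trial, with the same 40 centres, took much longer or somewhat less time than projected. The number of infants in the gestation range at other units does not have to be assumed, because the national records could supply it. The plan does not say that it will count them.

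**Working it through.** **Inputs.** Main trial of 4000 infants, 40 centres, 2-4 recruits per month, 50% uptake (all section 4.10.4); 18 months of pilot recruitment (sections 1 and 4.11.1).

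**1. Reproduce the plan's figure.** Months = 4000 / (40 × rate per centre).
- At 4 per month: 4000 / (40 × 4) = 25.
- At 2 per month: 4000 / (40 × 2) = 50.

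The stated range reproduces exactly, so 2-4 per month is being used as the mean rate per centre across all 40.

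**2. What this implies elsewhere.** At 50% uptake, 2-4 recruits per month need 2/0.5 = 4 to 4/0.5 = 8 eligible infants per month, averaged over 40 centres. The documents give no eligible count for any other unit.

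**3. Sensitivity to the other centres.** Let r be the pilot unit's monthly rate and let the other 39 units average k × r. The value of k is an assumption; the documents do not supply it. Months = 4000 / (r × (1 + 39k)).

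| k (assumed) | 1 + 39k | r = 4 | r = 2 |
|---|---|---|---|
| 1.25 | 49.75 | 20 | 40 |
| 1 | 40 | 25 | 50 |
| 0.75 | 30.25 | 33 | 66 |
| 0.5 | 20.5 | 49 | 98 |

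**4. Sampling error with identical centres (k = 1).** Exact Poisson 95% limits for n recruits are χ²(0.025; 2n)/2 and χ²(0.975; 2n + 2)/2, each divided by 18 to give a monthly rate.
- n = 18 × 2 = 36: limits 1.40 to 2.77 per month. Duration 4000/(40 × 2.77) = 36 to 4000/(40 × 1.40) = 71 months.
- n = 18 × 4 = 72: limits 3.13 to 5.04 per month. Duration 4000/(40 × 5.04) = 20 to 4000/(40 × 3.13) = 32 months.

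These intervals reflect chance at one unit only. They contain nothing for differences between units, which one unit cannot measure.

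**5. What could replace the assumption.** The database covers all neonatal admissions nationally, and the growth reference shows that such routine data have been analysed across units by week of gestation. A count of admissions in the trial's gestation range, unit by unit, is therefore within reach. No corrected duration can be computed here, because the documents report no such counts.

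**The case against.** The strongest reply is that the 25-50 months is an illustration in parentheses and not a decision rule. That is correct. A reader might infer that the pilot will declare the main trial feasible once 2-4 per month is reached, but no pass/fail rule is stated, and section 3 spreads feasibility over four aims.

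A reader might also infer that the plan looks only at a monthly count, or uses the national database only for outcomes. Neither is supported. Aim A2 already covers consent rates, and section 4.10.4 gives an expected uptake. Section 4.9.1 makes the data unit the default source of trial data, which takes in baseline items. What is absent is narrower: a count of potentially eligible infants per unit, and a projection that uses it.

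Nor do the documents show that 25-50 months is too short. Unit sizes are not given, the 40 centres are not named, and larger units could be chosen; k above 1 is possible.

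Two further points stand and limit the remedy. The recruited proportion is also a single-centre figure, and sections 2.2.1 and 2.4 describe varying attitudes to donor milk and variable practice, so acceptance may differ elsewhere. Routine records may not capture every exclusion in section 4.3.2, such as inability to randomise within 48 hours, so admission counts will tend to overstate eligible numbers.

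Finally, the projection could wait until the main-trial application. That is so, but section 4.10.4 already makes one, and it should carry its condition.

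**Conclusion.** The concern holds as a matter of generalisation; the arithmetic is sound. The 25-50 months depends on 40 centres averaging the pilot unit's rate, and a single-centre pilot cannot show that. Over assumed values of k from 1.25 down to 0.5, the projection moves from about 20-40 months to 49-98 months. Chance variation at the pilot unit alone would put it at 36-71 months after 36 recruits, or 20-32 months after 72. The values of k are illustrative, and the sampling intervals assume Poisson recruitment at a constant rate. The direction of any error is unknown. Randomisation, data collection and the primary analysis are unaffected.

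**What to change.** Revise section 4.10.4 as follows.
- State that 25-50 months is conditional on the centres matching the pilot unit on average.
- Replace the multiplication by 40 with a projection that sums, over candidate units, admissions at 25+0 to 31+6 weeks from the national database multiplied by the recruited proportion. Describe the admission counts as an upper approximation to eligible infants, because some exclusions may not be recorded.
- Take the recruited proportion from the pilot, building on the consent-rate estimate under aim A2, and report it with a 95% confidence interval.
- Show the projected duration over a range of proportions wider than that interval, since the interval omits differences in acceptance between units.

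A rule that judges feasibility on the lower confidence limit is not needed. It would be a matter of preference, and that limit would still describe only one unit.

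The cost is one database query and a short calculation, with no change to trial procedures. The projected duration may prove less favourable than the one now stated.
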